### 9.5.3. Analysis of PSA Levels

PSA50 is defined as the earliest attainment of a  $\geq 50\%$  decline in PSA relative to the baseline PSA obtained during the Screening period. The proportion of patients achieving PSA50 and time to PSA50 will be reported.

PSA90 is defined as the earliest attainment of a  $\geq 90\%$  decline in PSA relative to the baseline PSA obtained during the Screening period. The proportion of patients achieving PSA90 and time to PSA90 will be reported.

### 9.5.4. Analysis of the Antitumor Endpoints

Evaluation of prostate cancer response to treatment (RECIST v1.1 and PCWG3) is described in [Appendix 2](#).

The objective response rate (ORR) is defined as the proportion of efficacy-evaluable subjects with a response to treatment (defined as CR or PR). The number, percentage, and exact 95% CI will be presented.

The CR Rate is defined as the proportion of efficacy-evaluable subjects with a CR to treatment. The number, percentage, and exact 95% CI will be presented.

The duration of response (DOR) is defined as the time (in months) between initial response (CR or PR) and the date of first disease progression, relapse, or death for efficacy-evaluable subjects.

DOR will be analyzed using Kaplan-Meier methods. Further details on censoring rules will be described in the SAP.

The progression-free survival (PFS) is defined as the time (in months) between first study treatment dose date and the date of first disease progression or death from any cause. PFS will be analyzed using Kaplan-Meier methods. Further details on censoring rules will be described in the SAP.

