### 5.1. Subject Inclusion Criteria

1. Subject has provided informed consent and has signed an approved consent form that conforms to all applicable regulations and institutional guidelines.
2. Subject is  $\geq 18$  years of age at the time the Informed Consent Form (ICF) is signed.
3. Subject has histologically documented metastatic adenocarcinoma of the prostate confirmed by biopsy without neuroendocrine differentiation or small cell features.
4. Subject has a history of mCRPC.

5. Subject has R/R disease following treatment with at least 1 next-generation ARSI, e.g., enzalutamide, apalutamide, darolutamide, or abiraterone. Subjects with symptomatic and/or extensive visceral disease should have had prior therapy with  $\geq 1$  taxane regimen, unless considered ineligible for treatment with a taxane (per the treating Investigator) or have refused treatment with a taxane.
6. Subject has at least one measurable lesion according to Response Evaluation Criteria in Solid Tumors (RECIST) v1.1 criteria or evaluable bony disease. Lesions that have been previously irradiated will be considered measurable only if progression has been documented following completion of radiation therapy.
7. Subject has an Eastern Cooperative Oncology Group (ECOG) performance status of 0 to 2 ([Appendix 1](#)), and life expectancy of  $\geq 6$  months.
8. Subject agrees to take or continue luteinizing hormone-releasing hormone (LHRH) agonist or antagonist therapy or has undergone bilateral orchiectomy.
9. At least 2 weeks or five half-lives have elapsed, whichever is earliest, since the subject's last systemic therapy, including taxanes or other chemotherapy. At least one month has elapsed since systemic therapy with radionuclide pharmaceutical agents.
10. Subject has evidence of disease progression on or after their most recent systemic treatment, defined by any of the following criteria:
  - a. Increasing serum PSA levels as defined by the Prostate Cancer Working Group 3 (PCWG3), determined by 2 consecutive measurements (compared with a baseline or nadir value), with at least 7 days between each PSA measurement; or
  - b. Progression of measurable disease by RECIST v1.1, or progression of bony disease as defined by PCWG3 criteria.
11. Subject has a PSA level  $\geq 10$  ng/mL, or  $\geq 2$  ng/mL and  $\geq 50\%$  increase from nadir on prior therapy, whichever is lowest.
12. Subject has serum testosterone  $< 50$  ng/dL.

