## **8.2. Disease and Response Assessments**

Soft tissue (visceral and nodal) disease will be evaluated for evidence of radiographic response based on modified RECIST Version 1.1 criteria. Bone lesions will be followed and evaluated for evidence of radiographic progression based on PCWG3 criteria. See [Appendix 2](#) for details. Initial disease assessments to confirm subject eligibility and to serve as the response baseline can be taken from historical data as long as it was obtained within 28 days of the beginning of ONCT-534 treatment.

Tumor assessments will be performed as shown in the Schedule of Activities (Section 1.3). If a complete response (CR) or partial response (PR) is noted, confirmatory scans should be performed at least 4 weeks after the initial response was first documented.

All sites of disease should be followed, and the same methods used to detect lesions at baseline are to be used to follow the same lesions throughout the clinical study.

Tumor assessments for extra-skeletal disease should consist of clinical examination and appropriate imaging techniques. CT of the chest, abdomen, and pelvis should be performed with cuts of 5 mm or less in slice thickness contiguously. Spiral CT should be performed using a  $\leq 5$  mm contiguous reconstruction algorithm (i.e., as recommended by RECIST Version 1.1). Other studies (e.g., X-ray) may also be performed if clinically indicated. CT is preferred, but MRI may be used if clinically indicated, with cuts of 5 mm or less in slice thickness contiguously. Positron emission tomography (PET)/CT, using  $^{68}\text{Ga}$ -PSMA may be used if a local standard of care. If the CT performed as part of a PET/CT is of similar diagnostic quality to a diagnostic CT (with IV and oral contrast) then the CT portion of the PET/CT can be used for RECIST Version 1.1 measurements.

Radionuclide bone scanning (whole body) should be performed using  $^{99\text{m}}\text{Tc}$ -Methyl diphosphonate ( $^{99\text{m}}\text{Tc}$ -MDP) or hydroxydiphosphonate (HDP). Areas/lesions on bone scintigraphy that are suggestive can be assessed further with CT or MRI and followed separately, but such supplemental imaging should not be used to establish indicator lesions for the purposes of this study.

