## **9.2. Populations for Analysis**

The DLT-evaluable Population is defined as all subjects in the Phase 1 Dose Escalation part of the study who receive ONCT-534 and either complete the 28-day DLT observation period or discontinue the study early due to a DLT. Subjects will be grouped by the dose received.

The Safety Population is defined as all subjects who receive at least one dose of ONCT-534. Subjects will be grouped by the ONCT-534 dose received at study entry.

The Efficacy-evaluable Population is defined as all subjects who receive ONCT-534 and complete at least one post-treatment disease assessment and do not discontinue due to clinical evidence of disease progression without documentation prior to obtaining post-treatment disease assessment. Subjects will be grouped by dose received.

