#### Bone Lesions

For the purposes of this study, bone metastatic lesions should be recorded at baseline and followed during treatment using PCWG3 criteria (see below). Bone lesions should not be recorded as target or nontarget lesions to be followed by RECIST Version 1.1 criteria; this includes bone lesions with a soft tissue component and soft tissue lesions extending from a bone lesion.

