**Table 13: Evaluation of Best Overall Response: Subjects with Target (+/- Nontarget) Disease**

Target Lesions	Nontarget Lesions	New Lesions a	Overall Response
CR	CR	No	CR
CR	Non-CR/non-PD	No	PR
CR	Not evaluated	No	PR
PR	Non-PD or not evaluated	No	PR
SD	Non-PD or not evaluated	No	SD
Not Evaluated	Non-PD	No	NE
PD	Any	Yes or No	PD
Any	PD	Yes or No	PD
Any	Any	Yes	PD

a A New bone metastatic lesions should not be considered as a 'Yes' response; only new extra-skeletal lesions.

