**Table 14: Evaluation of Best Overall Response: Subjects with Nontarget Disease Only**

Nontarget Lesions	New Lesions	Overall Response
CR	No	CR
Non-CR-non-PD	No	Non-CR/non-PD a
Not all evaluated	No	NE
Unequivocal PD	Yes or No	PD
Any	Yes	PD

a 'Non-CR/non-PD' is preferred over 'stable disease' for nontarget disease since SD is increasingly used as endpoint for assessment of efficacy in some studies so to assign this category when no lesions can be measured is not advised.

Subjects with global deterioration of health status requiring discontinuation of treatment without objective evidence of disease progression at that time should be classified as having symptomatic deterioration. Every effort should be made to document the objective progression, even after discontinuation of treatment.

In some circumstances, it may be difficult to distinguish residual disease from normal tissue. When evaluation of CR depends on this determination, it is recommended that the residual lesion be investigated (fine needle aspiration/biopsy) prior to confirming the CR status.

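### ORR and CR rate are taken over all efficacy-evaluable subjects, including bone-only subjects who have no CR or PR category, so both rates are diluted by the bone-only share

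*Combined protocol and SAP*

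**What the plan says.** Section 9.5.4 fixes both denominators. For ORR: "The objective response rate (ORR) is defined as the proportion of efficacy-evaluable subjects with a response to treatment (defined as CR or PR". For complete response: "The CR Rate is defined as the proportion of efficacy-evaluable subjects with a CR to treatment". Each is to be reported as a number, a percentage and an exact 95% CI.

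Section 9.2 sets the population: "The Efficacy-evaluable Population is defined as all subjects who receive ONCT-534 and complete at least one post-treatment disease assessment". It also drops subjects who leave with undocumented clinical progression before any post-treatment assessment. It sets no condition on lesion type.

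Inclusion criterion 6 in Section 5.1 requires "at least one measurable lesion according to Response Evaluation Criteria in Solid Tumors (RECIST) v1.1 criteria or evaluable bony disease". Bone disease alone is enough.

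On assessment, Section 8.2 evaluates soft tissue for response, whereas for bone it says: "Bone lesions will be followed and evaluated for evidence of radiographic progression based on PCWG3 criteria". Appendix 2 adds: "Bone lesions should not be recorded as target or nontarget lesions to be followed by RECIST Version 1.1 criteria". That bar extends to bone lesions with a soft tissue component. The two tables that assign an overall response are Table 13, "Evaluation of Best Overall Response: Subjects with Target (+/- Nontarget) Disease", and Table 14, "Evaluation of Best Overall Response: Subjects with Nontarget Disease Only".

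The synopsis lists ORR and the complete response rate among the measures for the Phase 2 primary objective of preliminary antitumor activity.

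**The concern.** A bone-only subject (no target and no nontarget lesion at baseline) who is dosed and has one post-treatment assessment counts in both denominators. Under Appendix 2 that subject cannot count in either numerator. The plan does not find such a subject to be a non-responder. It gives the subject no response category at all.

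The reported rates then mix two things: how often assessable disease responds, and how many bone-only subjects happened to enrol. The same drug effect would give a different ORR in a cohort with more bone-only disease. ORR and CR rate are named under a Phase 2 primary objective and will be read as the drug's objective activity, so the interpretation of the absolute rates is what is at stake.

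**Working it through.** **1. The plan's own figures.** The documents give no expected ORR or CR rate and no bone-only share, so there is no figure of theirs to reproduce on this point. The nearest stated design is the Simon rule on PSA50 in Section 9.1.2: 9 then 7 subjects, at least 2/9 to continue, at least 5/16 to reject, for 10% against 40%. The rejection probability is the sum over x = 2 to 9 of P(X1 = x; 9, p) × P(X2 ≥ 5 - x; 7, p). At p = 0.10 it is 0.0159 and at p = 0.40 it is 0.815. A search over two-stage designs with alpha at most 0.025 and power at least 80% gives a minimum total of 16. The stated design reproduces, and ORR does not enter it.

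**2. Can a bone-only subject respond?**
- PR (Table 11) needs at least a 30% fall in the sum of target-lesion diameters. There are no target lesions.
- CR (Tables 11 and 12) needs target or nontarget lesions to disappear. There are neither.
- Tables 13 and 14 have no row for a subject with neither type of lesion.
- The PCWG3 bone section of Appendix 2 defines progression only, and says that a change in uptake intensity alone is not regression.

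So the answer is no. A subject with nontarget extra-skeletal disease only differs: Table 14 allows CR but has no PR row.

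**3. Size of the dilution.** Let b be the bone-only share and R the ORR (or C the CR rate) in subjects with RECIST-assessable disease. Then reported rate = R × (1 - b), and likewise C × (1 - b). All inputs are assumptions.

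| Rate in assessable disease | b = 10% | 20% | 30% | 40% | 50% | 60% |
|---|---|---|---|---|---|---|
| ORR 20% | 18% | 16% | 14% | 12% | 10% | 8% |
| ORR 30% | 27% | 24% | 21% | 18% | 15% | 12% |
| ORR 40% | 36% | 32% | 28% | 24% | 20% | 16% |
| CR rate 10% | 9% | 8% | 7% | 6% | 5% | 4% |

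**4. Effect on the dose comparison.** Take two cohorts of 16 and R = 30% in both, with q = R(1 - b). The SD of the difference in reported ORR is sqrt(2q(1 - q)/16). The part due to chance imbalance in bone-only subjects is R × sqrt(2b(1 - b)/16). The variance share is the squared ratio, which simplifies to Rb/(1 - q).

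| b | q | Total SD (points) | Imbalance SD (points) | Variance share |
|---|---|---|---|---|
| 10% | 0.27 | 15.7 | 3.2 | 0.03/0.73 = 4% |
| 30% | 0.21 | 14.4 | 4.9 | 0.09/0.79 = 11% |
| 60% | 0.12 | 11.5 | 5.2 | 0.18/0.88 = 20% |

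The rest is ordinary small-sample noise.

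**5. What the change does to an interval.** Exact (Clopper-Pearson) 95% limits, for an assumed cohort of 16 with 10 extra-skeletal and 6 bone-only subjects:
- 3 responders: 3/16 = 18.8% (4.0% to 45.6%) becomes 3/10 = 30.0% (6.7% to 65.2%).
- 1 CR: 1/16 = 6.3% (0.2% to 30.2%) becomes 1/10 = 10.0% (0.3% to 44.5%).
- If 2 of the 10 have nontarget disease only and all 3 responders have target lesions, the target-lesion row is 3/8 = 37.5% (8.5% to 75.5%).

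**The case against.** **The SAP may settle it.** Section 9.4 leaves further analysis detail to a SAP to be finalised before database lock, and its text is not in the document reviewed. It could restrict the denominator, so nobody can say for certain that the final tables will use the diluted one. But 9.5.4 already states both denominators, and within that section only the censoring rules for DOR and PFS are deferred. A general deferral does not undo a stated definition.

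**The rates are not biased.** A reader might infer that 9.5.4 yields a biased estimate. It does not. The proportion of all efficacy-evaluable subjects with CR or PR is a coherent quantity, estimated without bias. The shortfall exists only relative to response in assessable disease, which the protocol does not name as its target. This objection stands: the point concerns what is being estimated.

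**No decision turns on it.** A reader might infer that the go/no-go rule or the dose choice is compromised. The Simon rule uses PSA50, and ORR and CR rate are descriptive. Nor would restricting the denominator help the dose comparison much. With R = 30%, signal-to-noise improves by sqrt((1 - q)/(1 - R)): sqrt(0.73/0.70) = 1.02 at b = 10% and sqrt(0.88/0.70) = 1.12 at b = 60%. This also stands.

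**The split can be rebuilt.** Counts are reported, and Sections 9.4, 9.7 and 9.8 provide baseline tables, disease characteristics and listings. That helps a determined reader, but the headline rates and intervals would still follow the stated definition.

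**Conclusion.** The point holds as one of definition and interpretability. As 9.5.4 is written, bone-only subjects are in both denominators and can never be in a numerator, so each rate is multiplied by (1 - bone-only share). The direction and the factor follow from the documents. The size does not: the share is not given, and 27% to 12% for a 30% ORR rests on assumed shares of 10% to 60%.

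Three limits apply. Sample size, type I error and the Simon decisions are untouched. Bone-only imbalance accounts for about 4% to 20% of the variance of the difference between two cohorts of 16, again under assumed inputs. And it would be too strong to say that every subject without measurable disease is barred from responding, because those with nontarget extra-skeletal disease can reach CR under Table 14.

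**What to change.** In 9.5.4 and the SAP, before the SAP is final:

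- Report ORR and CR rate, each with an exact 95% CI, over one common denominator: efficacy-evaluable subjects with extra-skeletal disease (target or nontarget lesions) at baseline. Every CR then also counts in ORR and enters DOR.
- Show ORR in subjects with at least one target lesion as a subgroup row, because nontarget-only subjects have no PR route. Use target rather than measurable as the criterion, since Appendix 2 bars prostate and prostatic bed lesions as targets.
- State that bone-only subjects are not evaluable for RECIST response. PSA50 and PCWG3 bone progression, both already planned, describe them.
- Tabulate target, nontarget-only and bone-only counts by dose.
- Keep the all-evaluable rates as supportive, and leave the Efficacy-evaluable Population unchanged.

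Separate denominators for the two rates should be avoided. If ORR were limited to target-lesion subjects while the CR rate also took in nontarget-only subjects, then no responses among 8 target-lesion subjects and one CR among 2 nontarget-only subjects would give ORR 0/8 = 0% beside a CR rate of 1/10 = 10%. That conflicts with the definition of response in 9.5.4.

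The cost is wording only; baseline lesions are already recorded. The downside is smaller, unequal denominators and wider intervals, as in the change from 3/16 to 3/10 shown above.

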#### **9.5.5. Safety Analyses**

Safety assessments include DLTs, AEs, SAEs, clinical laboratory evaluations, vital sign measurements, ECGs, concomitant medications, and exposure to study drug.

Incidence of DLTs will be reported by Preferred Term and relationship to study drug.

AEs will be summarized by System Organ Class and Preferred Term. AEs will also be summarized by NCI-CTCAE (Version 5.0), severity, and relationship to study drug. Any Grade  $\geq 3$  AEs, and SAEs will also be summarized.

Incidences of laboratory abnormalities will be summarized with descriptive statistics.

Vital signs and ECGs will be summarized with descriptive statistics. Concomitant medications will be listed. Exposure to study drug will be summarized.

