Study Design ONCT-534 (previously known as GTx-534 or UT-34) is a dual-action androgen receptor inhibitor (DAARI) with a novel mechanism of action that includes inhibition of androgen receptor (AR) function and degradation of the AR protein mediated by interaction with the N-terminal domain (NTD) of the AR. ONCT-534 has demonstrated preclinical activity in prostate cancer models against both unmutated AR, and against multiple forms of AR alteration, including those with AR amplification, mutations in the AR ligand binding domain (LBD), and splice variants with loss of the AR LBD. Study ONCT-534-101 is a Phase 1/2, multi-center study to evaluate the safety, tolerability, antitumor activity, and pharmacokinetics (PK) of ONCT-534 in subjects with R/R histologically confirmed mCRPC who have relapsed or are refractory to at least one next-generation ARSI, such as enzalutamide, darolutamide, apalutamide, or abiraterone. The study will be separated into Phase 1 Dose Escalation and Phase 2 Dose Expansion portions. In all parts of the study, after a Screening period, eligible subjects with mCRPC will be enrolled to receive their assigned dose regimen of ONCT-534. ONCT-534 will be administered orally daily for 2 years or until documented progressive disease and no longer clinically benefiting from treatment, development of unacceptable toxicity, withdrawal of consent, end of study, or other discontinuation or withdrawal reasons, whichever occurs first (see Section 7.1 for details). Phase 1 Dose Escalation The Phase 1 portion of the study will use an adaptive Bayesian Optimal Interval (BOIN) Design (Liu and Yuan, 2014; Yuan et al., 2016). The anticipated number of subjects in the Phase 1 portion is approximately 27, in the expected 5 dose cohorts. The primary objectives are to assess the safety, tolerability, and dose-limiting toxicity (DLT) of ONCT-534 at escalating doses and to determine the MTD of ONCT-534 to inform the 2 dose levels or schedules to be tested in Phase 2. DLT will be assessed during the first 28 days of study treatment.	

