#### Primary Objectives:

- To assess the safety and tolerability of ONCT-534.
- To compare 2 dose levels or schedules of ONCT-534 and select the optimal dose for further study.
- To assess the preliminary antitumor activity of ONCT-534.

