### **8.3.8. Time Period and Frequency for Collecting AE and SAE Information**

Investigators will seek information on AEs at each subject contact. All AEs will be collected and recorded in the subject's medical record and on the Adverse Event eCRF as follows:

- From signing of ICF until first dose of study treatment: All SAEs, AEs due directly to study-related procedures/assessments, and AEs leading to subject/study discontinuation.
- From first dose of study treatment through 30 days after the last dose of study treatment OR initiation of subsequent anti-cancer therapies, whichever occurs first: All AEs and SAEs.
- Ongoing AEs/SAEs that are definitely, probably, or possibly related to study drug, should be followed until resolution or stabilization to  $\leq$  Grade 2, or returned to baseline status.

See Section 8.3.9 for instructions on recording AEs and SAEs, including abnormal laboratory values; pre-existing medical conditions; hospitalization; and disease progression, relapse, or disease-related death.

For each AE recorded on the Adverse Event eCRF, the Investigator will make an assessment of seriousness (Section 8.3.6), severity (Section 8.3.4), and causality (Section 8.3.5).

SAEs are required to be reported by the Investigator to the Sponsor immediately (i.e., no more than 24 hours becoming aware of the event). See Section 8.4 for reporting instructions.

Investigators are not obligated to actively seek AE or SAE collection after conclusion of the study participation. However, if the Investigator learns of any SAE, including a death, at any time after a subject has been discharged from the study and he/she considers the event to be reasonably related to the study drug or study participation, the Investigator must promptly notify the Sponsor.

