## 9.4. Statistical Analysis Methods

Further details of the statistical analyses will be described in the Statistical Analysis Plan (SAP). The SAP will be finalized prior to database lock.

All collected data will be reported using summary tables and figures, as appropriate. Tabulations will be produced for disposition, demographic, baseline, efficacy, and safety. Summaries will be grouped by dose level in Phase 1 and expansion dose levels in Phase 2. Categorical variables will be descriptively summarized using number and percentage of subjects, with continuous variables descriptively summarized using mean, standard deviation, median, minimum, and maximum. For time to event variables, percentages of subjects experiencing the event will be presented and the median time to event will be estimated using Kaplan-Meier methodology. As appropriate, 95% confidence intervals (CIs) will be presented.

No type I error adjustments for multiple testing are planned. No hypothesis testing will be performed on secondary or exploratory endpoints.

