#### **10.1.4. Safety Oversight and Safety Review Committee**

Safety oversight will be the responsibility of the SRC, which is a multidisciplinary committee with the objectives to evaluate safety data, provide input and recommendations on study conduct and risk mitigation related to the following concerns:

- Are there any newly identified or potential risks with study treatment?
- Has the benefit/risk profile of ONCT-534 changed?
- Should the study be amended, paused, or stopped?
- In collaboration with Investigators, should dose escalation proceed to the next dose level?
- What is the appropriate RP2D?

The SRC is composed of cross-functional representatives including the Sponsor and the Phase 1 Study Investigators. The SRC will convene as needed to review cumulative data and to make recommendations for study conduct. The SRC will review the safety data, and any PK, pharmacodynamics, and efficacy data from each dose cohort in Phase 1 and will make the decision to move to the next dose level based upon their review of the data. Based on the totality of safety, PK and clinical data, the SRC may recommend dose level(s) between or above the initial dose levels, or alternate dosing schedule(s). The SRC will also propose the 2 dose levels or schedules to be evaluated in the Phase 2 expansion portion based upon available safety, PK, pharmacodynamics, and efficacy data. The SRC activities for this study are described in the SRC Charter.

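### AE percentages by dose cover unequal time at risk if time on drug differs; add a common-window incidence and exposure-adjusted rates to the dose comparison

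*Combined protocol and SAP*

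**What the plan says.** - Section 9.5.5: "AEs will be summarized by System Organ Class and Preferred Term". AEs are also summarized by grade and relationship, with separate summaries of Grade 3 or higher AEs and of SAEs. Exposure to study drug is summarized, but not linked to AE incidence.
- Section 9.4 gives the scale, "Categorical variables will be descriptively summarized using number and percentage of subjects", and the grouping, "Summaries will be grouped by dose level in Phase 1 and expansion dose levels in Phase 2".
- Section 8.3.8 collects all AEs from first dose "through 30 days after the last dose of study treatment OR initiation of subsequent anti-cancer therapies, whichever occurs first".
- Treatment is open-ended within a cap. Synopsis: "ONCT-534 will be administered orally daily for 2 years or until documented progressive disease" without further clinical benefit, or another stopping reason. Section 6.2 puts the cap at 108 weeks.
- A Phase 2 primary objective (Section 3.2) reads: "To compare 2 dose levels or schedules of ONCT-534 and select the optimal dose for further study". No method is given for the safety side of that comparison.
- Section 10.1.4: "The SRC will convene as needed to review cumulative data and to make recommendations for study conduct". The SRC also proposes the two Phase 2 doses from safety, PK, pharmacodynamic and efficacy data.
- Section 9.2 groups the Safety Population by dose at study entry. Section 4.1.3 offers Phase 1 subjects escalation to a higher dose after their DLT window.

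**The concern.** The percentage of subjects who ever have an AE rises with time observed. Here that time is time on drug plus up to 30 days, which can differ by dose for reasons other than toxicity. A dose that delays progression keeps subjects on drug, and under observation, for longer. At the SRC's interim look, a Phase 1 level opened early has been followed longer than one opened late. In Phase 2, one cohort may also be paused while the other enrols (Section 9.1.2). The stated AE tables include no common window, rate per time at risk or time-to-event summary.

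At stake is how the safety input to dose choice is read, at the SRC's proposal of the Phase 2 doses and at the final Phase 2 comparison. Intra-patient escalation adds a second problem: an event at a higher dose is tabulated under the lower starting dose.

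**Working it through.** **The plan's own figures.** The concern disputes none of them, but 16 per dose sets the precision of the comparison. For the Simon rule, P(reject | p) = sum over x = 2 to 9 of Bin(x; 9, p) × P(Bin(7, p) ≥ 5 − x). This gives 0.0159 at p = 10% and 0.815 at p = 40%, in line with the stated 0.025 and 80%. The BOIN boundaries at a target of 0.3 also reproduce (0.236 and 0.359). They act on DLTs within 28 days at every dose, so unequal follow-up does not enter them.

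**Phase 2, equal toxicity and unequal time on drug.** Assumed, not in the documents: constant AE hazard λ = 0.05 per month at both doses; exponential time on drug with median m = 3 or 6 months; observation 30 days past last dose. From the plan: cap of 108 weeks = 24.8 months; 30 days = 0.986 month. With μ = ln 2 / m:

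P(AE) = 1 − e^(−0.986λ) × [ μ/(μ+λ) + λ/(μ+λ) × e^(−24.8(λ+μ)) ]

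- m = 3 (μ = 0.231): 1 − 0.952 × 0.822 = 22%.
- m = 6 (μ = 0.116): 1 − 0.952 × 0.703 = 33%.
- Gap: 11 points with no difference in toxicity. For 4 versus 6 months it is 26% versus 33%.

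**Other hazards** (same medians, ignoring the 30-day tail): 5% per 28 days gives 19% versus 32%; 10% per 28 days gives 33% versus 50%. The gaps are 13 and 17 points.

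**Against chance.** SE of the difference at 16 per dose = √(0.22×0.78/16 + 0.33×0.67/16) = 0.157, or 15.7 points. The 11-point gap is 0.7 SE, or under two subjects (0.11 × 16 = 1.8).

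**Early AEs only.** With the hazard confined to the first 2 months, 3 versus 6 months gives about 17.2% versus 17.7% at 0.1 per month, and 31.4% versus 32.2% at 0.2. The gap is about 1 point or less.

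**The other direction.** Suppose the dose with the 3-month median has twice the hazard (λ = 0.10) and its shorter time reflects stopping for toxicity. Its crude incidence is 1 − 0.906 × 0.698 = 37%, against 33% for the other dose. A twofold hazard ratio then appears as a ratio of 1.1.

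**Phase 1 at an SRC look.** Assume each level starts 28 days after the one before, subjects stay on drug, and the look falls when level 5 completes its DLT window. Follow-up is then 140, 84, 56 and 28 days at levels 1, 3, 4 and 5. With hazard 0.1 per 28 days at every level, 1 − e^(−0.1t/28) gives 39%, 26%, 18% and 10%. If level 5 has twice the hazard, it shows 1 − e^(−0.2) = 18.1%. That is below level 3, but exactly tied with level 4.

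**What the remedy does.** Under the Phase 2 assumptions with λ = 0.05, expected time at risk to first event or window end is P/λ = 4.3 and 6.6 months, so the rate is 0.05 per month at both doses. For incidence through Week 12 (2.76 months), replace 24.8 in the formula by 2.76 − 0.986 = 1.77. The result is 11.5% versus 12.1%, so the 11-point gap falls below 1 point.

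**The case against.** The case against is substantial, and most of it limits the scope of the point.

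- A reader might infer that dose selection rests on unequal harm windows. The documents do not support that. Escalation, de-escalation, elimination and the MTD use DLTs in a fixed 28-day window. No rule selects a dose on AE percentages, and the SRC weighs PK, pharmacodynamic and efficacy data too.
- A reader might also infer that the tables will reverse the true order of toxicity. In Phase 1 that needs a wide contrast and an assumed cut date. The 39% concerns a level that may hold one subject under accelerated titration, who may since have escalated. Adjacent levels 4 and 5 only tie.
- The Phase 1 stagger largely fades from the final tables. Section 7.5 ends the study only after the last subject stops treatment and completes the 30-day follow-up. Barring early termination, it matters only at the interim look.
- The Phase 2 medians are assumed, and the direction of bias is not fixed.
- Exposure is summarized in the same section, so a reader would see unequal time on drug. Section 9.4 defers further detail to an SAP whose content cannot be seen here.

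What remains: a separate exposure summary does not put AE incidence on a common footing. The SAP need only be final before database lock, which can fall after the SRC has proposed the Phase 2 doses. Chance variation is larger than the bias in the main example, but that is no reason to leave in a systematic error that is cheap to remove.

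**Conclusion.** The point holds as a limited one. The only stated AE summary by dose is a crude percentage over a window as long as treatment plus 30 days. It is not like-for-like if time on drug differs by dose. This affects the Phase 2 dose comparison and the SRC's cumulative review when it proposes the Phase 2 doses. It does not affect escalation or the MTD.

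The size is modest and depends on assumptions: about 11 points in the main example, 13 to 17 under the other hazards tried, and about 1 point or less if AEs are confined to the first 2 months. The sign depends on why time on drug differs: longer disease control overstates a dose's relative toxicity, and early stopping for toxicity understates it. The grouping by entry dose alongside permitted escalation is documented and needs no such assumption. This is a worthwhile improvement to the analysis, not a flaw that invalidates the design.

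**What to change.** In Section 9.5.5 and the SAP, for between-dose summaries of AEs, Grade 3 or higher AEs and SAEs, keep the crude percentages and add:

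1. Incidence in a common window from first dose: Days 0-28, and for Phase 2 also through Week 12 among subjects whose first dose was early enough before the data cut.
2. Exposure-adjusted rates per subject-month at risk, with time at risk ending where the Section 8.3.8 window ends.
3. For Phase 1 subjects who escalate, events and time at risk assigned to the dose at onset, or censored at the dose change. Without this, rates over the full window would still charge higher-dose events and time to the starting dose.

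Supply these tables to the SRC when it proposes the Phase 2 doses, and use them beside the crude tables for the Phase 2 comparison.

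The cost is wording and a few extra tables. The DLT and Section 8.3.8 windows already require onset and dosing dates, and Section 7.1 collects the date of next systemic therapy. The downside is that exposure-adjusted rates assume a roughly constant hazard, which is why the fixed-window incidence sits beside them, and they are unstable in cohorts of 1 to 3 subjects.
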